6.12.2. Adverse Events

6.12.2.1. Analysis of Adverse Events

Adverse events are classified based on MedDRA. A TEAE is defined as an event that first occurred or worsened in severity after baseline and on or prior to the date of the last visit within the treatment period. Both the date/time of the event and the date/time of the dose (that is, injection) are considered when determining TEAEs. The MedDRA Lowest Level Term (LLT) will be used in the treatment-emergent computation. The maximum severity for each LLT during the baseline period will be used as baseline severity (in some cases baseline period is a single time point). Events with a missing severity during the treatment period will be considered treatment emergent. The treatment period will be included as post-baseline for the analysis. If an event is pre-existing during the baseline period but it has missing severity, and the event persists during the treatment period, then it will be considered as treatment-emergent, regardless of the post-baseline level of severity. Adverse events with a particular LLT will be classified as treatment-emergent if they first start on or after the first dose date in the treatment period (i.e., a

patient has no pre-existing conditions with that LLT), or if the severity is greater than the pre-treatment severity for that LLT.

A follow-up emergent adverse event (FEAE) is defined as an event that first occurred or worsened in severity after the date of Week 104 (Visit 29) or the ETV. The MedDRA LLT will be used when classifying FAEs as follow-up emergent. For AEs that are ongoing at the date of Week 104 (Visit 29) or ETV, the maximum severity recorded for each LLT on the date of Week 104 (Visit 29) or ETV will be used as the follow-up baseline severity for that lowest level term.

An overview table will be provided and will include the frequency and percentage of patients who experienced a TEAE, TEAE by maximum severity, a treatment-emergent AESI, SAE, died, or discontinued from the study due to an AE (including death) will be summarized by treatment group for each treatment period. A listing will be provided as well.

The number and percentage of patients, and the number of events (where applicable) will be presented, by treatment group for each treatment period, separately. When the SOC is presented, events will be ordered by decreasing frequency in the ixekizumab dose group, within SOC. When the SOC is not presented, the events will be ordered by decreasing frequency in the overall group followed in the order of ixekizumab Q4W then adalimumab Q2W. For incidence counts, each patient will be counted only once within each Preferred Term and within each SOC. Percentages will be based on the number of patients in a particular treatment group. For events that are gender-specific, the denominator and computation of the percentage will include only patients from the given gender.

The following summary tables will be provided for the OLT Period (Safety Population), OLE Period (OLE Period Population and OLE Switcher Population), and LTE Period (LTE Safety Population):

- An overview summary of AEs
- TEAEs, by SOC and Preferred Term
- TEAEs, by Preferred Term
- TEAEs by maximum severity, by SOC and Preferred Term

The following summary tables will be provided for the PTFU Period (PTFU Population):

- FAEs, by Preferred Term

By-patient listing of all TEAEs will be provided.

If a partial or completely missing AE start date/time or end date/time is present the following imputation rules will be utilized in the analysis:

- For the start date:
 - If year, month, and day are missing, then use the earlier of the patient's first visit date or the consent date.
 - If either month or month and day are missing, then use January 1.
 - If only day is missing, impute the first day of the month.

- For the start time:
 - Impute as 23:59
- For the end date:
 - If year, month, and day are missing, then use the patient's last visit date in the follow-up period.
 - If either month or month and day are missing, then use December 31.
 - If only day is missing, then use the last day of the month.
 - The imputed date will not be beyond the patient's last visit date in the follow-up period.
- For the end time:
 - Impute as 23:59.
- If there is any doubt, the event will be flagged as treatment-emergent or follow-up emergent according to the corresponding study period. If a follow-up emergent event was already counted as treatment-emergent during the prior treatment period, it will not be counted as a follow-up emergent event.

6.12.3. Deaths, Other Serious Adverse Events, and Adverse Events Leading to Study Treatment Discontinuation

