- CCI every 2 weeks (Q2W) CCI
- CCI Q2W CCI

Study RHCG will be conducted in 4 parts:

- Open-label treatment (OLT) Period: 16 weeks.
- OLE Period: 88 weeks.
- LTE Period: 160 weeks.
- Post-treatment follow-up (PTFU; Visits 801, 802, and 803): 4 to 12 weeks after the last visit.

Participants who complete the OLT period may continue to the OLE period of the study. Participants who complete the OLT and OLE periods of this study may participate in an open-label LTE period.

Participants receiving adalimumab during the OLT period who did NOT attain a JIA ACR 30 response at Week 16 will be switched to ixekizumab in the OLE period. Participants receiving adalimumab during the OLT period who did attain a JIA ACR 30 response at Week 16 will be given the option to switch or not to switch to ixekizumab in the OLE period. The decision to switch for participants who achieved a JIA ACR 30 response will be left to the participant/participant's caregiver and investigator. A switch from adalimumab to ixekizumab during the OLE period may also occur at any other visit after Week 16 based on the participant/participant's caregiver and investigator's decision. After switching to ixekizumab, the participants will not have the option to resume adalimumab treatment during the remainder of the trial participation. Any adalimumab participants that complete the open label extension period of the study will be reassigned to ixekizumab starting with Treatment Period 3 (refer to Section 6.1 for additional details). Adalimumab participants who choose not to switch to ixekizumab at the end of the open label period will enter the PTFU and be considered study completers.

Participant who do not enroll in the LTE study or discontinued early (participants who have received at least 1 dose of study drug) should enter the PTFU period and complete through Visit 802. Participants may be followed beyond Visit 802 for continued monitoring of their neutrophil counts if determined by the sponsor/investigator that additional monitoring is needed. If a participant discontinues study drug early, the participant will complete the early termination visit (ETV) and then enter the PTFU period.

Study Population:

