PK sample		X		X		X	X	At visits where study drug will be administered, PK samples should be collected prior to administration of study drug.

Abbreviations: AE = adverse event; AESI = adverse events of special interest; BP = blood pressure; d = days; EQ-5D-Y = European Quality of Life-5 Dimensions-Youth; ESR = erythrocyte sedimentation rate; HBcAb = hepatitis B core antibody; HBsAb = hepatitis B surface antibody; HBsAg = hepatitis B surface antigen; HBV = hepatitis B virus; HCV = hepatitis C virus; HIV = human immunodeficiency virus; HLA-B27 = human leukocyte antigen-B27; hsCRP = high-sensitivity C-reactive protein; IBD = inflammatory bowel disease; JIA = juvenile idiopathic arthritis; LEI = Leeds Enthesitis Index; NK = natural killer; PPD = purified protein derivative; PK = pharmacokinetics; Q2W = every 2 weeks; Q4W = every 4 weeks; RF = rheumatoid factor; TB = tuberculosis; V = study visit; W = study week.

Note: Due to blood volume restrictions, some laboratory tests may not be collected. Laboratory samples are recommended to be collected as described in the sponsor-provided weight-based prioritization chart.

Table RHCG.2.2. Schedule of Activities – Open-Label Extension Period (V8 through V20)

Visit No	Open-Label Extension Treatment Period												Notes		
	V8	V9 (TV)	V10 (TV)-	V11	V12 (TV)	V13 (TV)	V14	V15 (TV)	V16 (TV)	V17	V18 (TV)	V19 (TV)	V20		
Study Week	W20	W24	W28	W32	W36	W40	W44	W48	W52	W56	W60	W64	W68		
Study Days (Approximately)	140 ± 7d	168 ± 7d	196 ± 7d	224 ± 7d	252 ± 7d	280 ± 7d	308 ± 7d	336 ± 7d	364 ± 7d	392 ± 7d	420 ± 7d	448 ± 7d	476 ± 7d		
Immunization record				X			X			X				Immunizations occurred during the participation in the study.	
Physical examination				X			X			X				Excluding pelvic, rectal, and breast examinations.	
Height	X			X			X			X					
Weight	X	X	X	X	X	X	X	X	X	X	X	X	X		
Occipital frontal circumference measurement	X			X			X			X				Only in children up to 3 years of age.	
Habits										X				Including caffeine, alcohol, and tobacco consumption. Assessment only for participants 12 years of age or older.	
Vital signs (BP, pulse, body temperature)	X	X	X	X	X	X	X	X	X	X	X	X	X	BP and pulse should be measured at least pre-injection.	
Concomitant medications	X			X			X			X			X		
AEs	X	X	X	X	X	X	X	X	X	X	X	X	X	See Section 9.2.2.3 for a complete list of adverse events of special interest (AESI). IBD events will be adjudicated. During TV AEs are collected if spontaneously reported.	

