Adverse events (AEs)			X			X			X			X	See Section 9.2.2.3 for a complete list

Note: Due to blood volume restrictions, some laboratory tests may not be collected. Laboratory samples are recommended to be collected as described in the sponsor-provided weight-based prioritization chart.													
Visit No	V43	V44	V45	V46	V47	V48	V49	V50	V51	V52	V53	V54	Notes
Study Week	W160	W164	W168	W172	W176	W180	W184	W188	W192	W196	W200	W204	
Study Days (Approximately)	1120 ± 7d	1148 ± 7d	1176 ± 7d	1204 ± 7d	1232 ± 7d	1260 ± 7d	1288 ± 7d	1316 ± 7d	1344 ± 7d	1372 ± 7d	1400 ± 7d	1428 ± 7d	
Treatment Visits	X	X		X	X		X	X		X	X		
													of AESIs. IBD events will be adjudicated. Investigators will assess the AEs during the regular visits.
Dispense study intervention	X	X	X	X	X	X	X	X	X	X	X	X	See Section 6.1 for details. 
 Participants CCI who have opted for at-home administration will have ixekizumab dispensed during the regular visits only (i.e., every 12 weeks). The rest of the participants will have the study drug dispensed during both the treatment visits and regular visits (that is, every 4 weeks).
Train on ixekizumab administration			X			X			X			X	Only for participants CCI who opt for at-home administration and/or for their caregivers. See Section 7.1 for details. This training will occur throughout the study for those participants who reach CCI and opt for at-home administration.
Administer ixekizumab	X	X	X	X	X	X	X	X	X	X	X	X	See Sections 7.1 for on-site and at-home administration details and for treatment regimens. During regular visit, all participants (regardless of their weight) will receive ixekizumab injection on site.

Note: Due to blood volume restrictions, some laboratory tests may not be collected. Laboratory samples are recommended to be collected as described in the sponsor-provided weight-based prioritization chart.													
Visit No	V43	V44	V45	V46	V47	V48	V49	V50	V51	V52	V53	V54	Notes
Study Week	W160	W164	W168	W172	W176	W180	W184	W188	W192	W196	W200	W204	
Study Days (Approximately)	1120 ± 7d	1148 ± 7d	1176 ± 7d	1204 ± 7d	1232 ± 7d	1260 ± 7d	1288 ± 7d	1316 ± 7d	1344 ± 7d	1372 ± 7d	1400 ± 7d	1428 ± 7d	
Treatment Visits	X	X		X	X		X	X		X	X		Treatment visits are intended only for the on-site administration of the ixekizumab for the participants CCI [REDACTED] who have opted for on-site administration.
Clinician-Reported Measures													
Joint Assessment			X			X			X			X	

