6.12.1. Extent of Exposure

Duration of exposure to study treatment (defined as time since first injection of study treatment in days) will be summarized by treatment group during the OLT Period and the OLE Period.

The duration of exposure during the **OLT Period for the Safety Population** will be calculated as:

(Date of last study visit in OLT Period – Date of first injection of study treatment + 1)

The duration of exposure on initially assigned treatment for the **OLE Period Population** will be calculated as:

Date of last visit on initially assigned treatment – Date of first dose in OLE Period + 1

The duration of exposure during the **OLE Period** for the OLE Switcher Population will be calculated as:

(Date of last study visit in OLE Period – The first date of switch to ixekizumab + 1)

The duration of exposure during the **LTE Period** for LTE Safety population will be calculated as:

(Date of last study visit in LTE Period – Date of first injection of study treatment + 1)

Descriptive statistics will be provided for patient days of exposure and the frequency of patients falling into the following different exposure ranges (that is, only the exposure ranges that fall within the treatment period will be presented) will be summarized:

- $>0, \geq 7 \text{ days}, \geq 14 \text{ days}, \geq 30 \text{ days}, \geq 60 \text{ days}, \geq 90 \text{ days}, \geq 120 \text{ days}, \geq 183 \text{ days}, \geq 365 \text{ days.}$
- $>0 \text{ to } <7 \text{ days}, \geq 7 \text{ to } <14 \text{ days}, \geq 14 \text{ to } <30 \text{ days}, \geq 30 \text{ to } <60 \text{ days}, \geq 60 \text{ to } <90 \text{ days}, \geq 90 \text{ to } <120 \text{ days}, \geq 120 \text{ to } <183 \text{ days}, \geq 183 \text{ to } <365 \text{ days}, \geq 365 \text{ days.}$

Overall exposure for each treatment group within the OLT Period and the OLE Period for respective populations will also be summarized in total patient years. This will be calculated as follows:

Exposure in patient years = Sum of duration of exposure with the defined treatment period (for all patients in treatment group) / 365.25.

A listing of study drug exposure will also be provided.

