A change from baseline summary analysis will be presented for the Safety Population, the OLE Period Population, and the LTE Safety Population. A shift table will be produced showing the number and percentage of patients shifting from baseline score to a maximum postbaseline score in categories of <6 and ≥6 for the Safety Population, the OLE Period Population, and the LTE Safety Population.

6.12.8. *Columbia-Suicide Severity Rating Scale (C-SSRS)*

The C-SSRS is an assessment tool that evaluates suicidal ideation and behavior. Information on the C-SSRS scale can be found through the following link: http://cssrs.columbia.edu/wp-content/uploads/C-SSRS_Pediatric-SLC_11.14.16.pdf (RFMH 2008).

Specifically, the following outcomes are C-SSRS categories and have binary responses (yes/no). The categories have been re-ordered from the actual scale to facilitate the definitions of the composite and comparative endpoints, and to enable clarity in the presentation of the results.

Category 1 – Wish to be Dead

Category 2 – Non-specific Active Suicidal Thoughts

Category 3 – Active Suicidal Ideation with Any Methods (Not Plan) without Intent to Act

Category 4 – Active Suicidal Ideation with Some Intent to Act, without Specific Plan

Category 5 – Active Suicidal Ideation with Specific Plan and Intent

Category 6 – Preparatory Acts or Behavior

Category 7 – Aborted Attempt

Category 8 – Interrupted Attempt

Category 9 – Actual Attempt (non-fatal)

Category 10 – Completed Suicide

Self-injurious behavior without suicidal intent is also a C-SSRS outcome (although not suicide-related) and has a binary response (yes/no).

Composite endpoints based on the above categories are defined below.

- **Suicidal ideation:** A “yes” answer at any time during treatment to any 1 of the 5 suicidal ideation questions (Categories 1-5) on the C-SSRS.
- **Suicidal behavior:** A “yes” answer at any time during treatment to any 1 of the 5 suicidal behavior questions (Categories 6-10) on the C-SSRS.
- **Suicidal ideation or behavior:** A “yes” answer at any time during treatment to any 1 of the 10 suicidal ideation and behavior questions (Categories 1-10) on the C-SSRS.

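### Safety tables give crude patient percentages for periods of 16, 88 and 160 weeks, with no defined incidence rate and no patient-years for the LTE

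*SAP*

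**What the plan says.** The Protocol Synopsis (Treatment Arms and Duration) sets the periods: "Open-label treatment (OLT) Period: 16 weeks", "OLE Period: 88 weeks" and "LTE Period: 160 weeks".

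For adverse events, SAP 6.12.2.1 says: "The number and percentage of patients, and the number of events (where applicable) will be presented, by treatment group for each treatment period, separately". It bases percentages on the number of patients in the treatment group. SAEs (6.12.3.2) and discontinuations due to AEs (6.12.3.3) take the same form. Table RHCG.6.16 lists the AESIs as treatment-emergent event tables for each period.

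Four further provisions bear on how those percentages can be read.

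- **Follow-up in the OLE.** SAP 6.1.2.2.1 keeps adalimumab data only up to the switch to ixekizumab. Later data go to the Switcher Population.
- **Person-time.** SAP 6.12.1 plans total patient-years as "Overall exposure for each treatment group within the OLT Period and the OLE Period" and does not name the LTE. The LTE duration formula subtracts the date of the first injection of study treatment, whereas the OLE formula specifies the first dose in that period.
- **Rates.** SAP 6.12 says categorical safety measures, and switcher data in particular, will be summarized with incidence rates. SAP 6.15.1 repeats the term for the DMC. Neither defines it, and 6.12.12.2.1 uses incidence to mean a percentage. A rate per 100 patient-years is specified only in 6.12.12.2.3, for hypersensitivity and injection-site events by antibody status.
- **Ascertainment.** AEs are collected at every OLT visit. For OLE treatment visits, Protocol Table RHCG.2.2 says: "During TV AEs are collected if spontaneously reported". For the LTE, Table RHCG.2.4 says: "Investigators will assess the AEs during the regular visits".

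For the CDI-2, SAP 6.12.7 plans a table of patients "shifting from baseline score to a maximum postbaseline score in categories of <6 and ≥6", alongside a change-from-baseline summary.

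**The concern.** A crude percentage estimates the chance of at least one event during whatever time was observed. When that time differs tenfold between periods, the same underlying risk produces very different percentages. The LTE objective is long-term safety and tolerability, so readers will naturally set the LTE column beside the OLT and OLE columns.

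The problem also exists inside a single OLE table. A switch is allowed at any OLE visit, so the adalimumab column can rest on systematically shorter follow-up than the ixekizumab column next to it.

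A maximum taken over repeated assessments has a similar weakness. By the Schedule of Activities, the CDI-2 has 3 post-baseline assessments in the OLT, 8 in the OLE and 14 in the LTE, so the chance that the maximum crosses the cut-off grows with the number of looks.

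**Working it through.** **Period lengths.** From visit weeks: 16 − 0 = 16, 104 − 16 = 88, 264 − 104 = 160. These match the Synopsis. In years (weeks × 7/365.25) they are 0.307, 1.687 and 3.066.

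**Effect of length alone.** The documents give no AE rates, so the hazard is an assumption shown over a range. With a constant hazard λ and full follow-up, the crude percentage is 1 − exp(−λ × years).

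| λ per 100 patient-years | OLT | OLE | LTE | LTE ÷ OLT |
|---|---|---|---|---|
| 2 | 0.6% | 3.3% | 5.9% | 9.7 |
| 20 | 5.9% | 28.6% | 45.8% | 7.7 |
| 100 | 26.4% | 81.5% | 95.3% | 3.6 |

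Ratios use unrounded percentages. The underlying risk is identical across each row.

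**Unequal follow-up within the OLE.** At 20 per 100 patient-years, 88 weeks gives 28.6%. If adalimumab follow-up before the switch averaged 44 weeks (assumed), the percentage would be 1 − exp(−0.2 × 44 × 7/365.25) = 15.5%. At 22 weeks it would be 8.1%. The arms would differ in the table with no difference in risk.

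**First opposing effect: AE questioning.** Scheduled post-baseline AE assessments number 5 in the OLT, 8 regular visits in the OLE and 14 in the LTE (Visit 30, then every third visit from 33 to 69). That is 16.3, 4.7 and 4.6 per year. If only half of events were captured in the OLE and LTE (assumed), the 20 per 100 row would read 5.9/15.5/26.4%. To cancel the length effect entirely, capture would have to fall to 16/88 = 18% of the OLT level in the OLE, or 16/160 = 10% in the LTE.

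**Second opposing effect: the baseline.** SAP 6.12.2.1 counts an event only if the term is new or worse than its baseline severity. SAP 6.1.2.3 runs the LTE baseline period from Visit 1. If an earlier event of the same term and severity removes a patient from the count, then at 20 per 100:

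- OLE: exp(−0.2 × 0.307) × 28.6% = 0.9405 × 28.6% = 26.9%
- LTE: exp(−0.2 × 1.993) × 45.8% = 0.6712 × 45.8% = 30.8%

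The LTE-to-OLT ratio falls from 7.7 to about 5.2. At 100 per 100 the LTE figure is about 13%, below the OLT's 26.4%. This applies to individual terms, not to the row for any TEAE.

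**LTE person-time.** Read literally, the LTE formula in SAP 6.12.1 runs from Week 0: up to 264 weeks instead of 160. A rate using it would be 160/264 = 61% of its proper value. The exposure bands also stop at 365 days, while the LTE lasts 160 × 7 = 1,120 days.

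**What a rate does.** If 80 ixekizumab patients all completed (assumed), person-time would be about 24.5, 134.9 and 245.3 patient-years. At a hazard of 50 per 100 patient-years, the rate is about 50 in every period, while the crude percentages are 14.2, 57.0 and 78.4.

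**The case against.** The strongest reply is that the tables are descriptive, presented by period, and not meant for comparison across periods. The SAP also plans event counts where applicable, listings of all TEAEs, an LTE duration summary and an exposure listing, from which approximate rates could be rebuilt. Most of this stands as fact. It does not answer the unequal follow-up between arms within an OLE table, and the wording of the LTE duration formula makes a rebuilt LTE rate unreliable.

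A second reply is that the SAP does promise incidence rates and cites compound-level standards that may define them. A reader might infer from the detailed sections that the plan has no rates at all outside the antibody analysis. The documents do not support that. The supportable criticism is that the term is used without a definition and sits beside sections that specify percentages only.

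A third reply is that AE collection is continuous from consent to the end of participation (Protocol 9.2.1 and 9.2.2), with SAEs reported within 24 hours. That stands. Sparser prompting plausibly affects recall of mild events; nothing suggests it affects SAEs or discontinuations.

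For the CDI-2, the planned change-from-baseline summary already offsets part of the concern about the maximum.

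**Conclusion.** The point holds as a gap in specification and a better available method. The planned percentages confound risk with length of follow-up, both across periods and between arms within the OLE. The SAP does not define the rate that would separate them and leaves the LTE without total patient-years.

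Over assumed hazards of 2 to 100 per 100 patient-years, length alone would multiply the percentage 9.7-fold to 3.6-fold from OLT to LTE. Those figures rest on a constant hazard, complete follow-up, equal capture and no baseline exclusion.

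A reader might infer that long-term risk will necessarily appear to climb. That goes too far: less frequent AE questioning and the LTE baseline from Visit 1 both lower later figures, and for a very common recurring term the LTE percentage could fall below the OLT one. The net direction is not fixed. The primary efficacy analysis is unaffected.

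**What to change.** 1. In SAP 6.12, define the incidence rate as the number of patients with a first event per 100 patient-years at risk, with a 95% confidence interval. Person-time runs to the first event or the end of the period, and for adalimumab patients in the OLE it is censored at the switch.
2. In 6.12.2, 6.12.3 and Table RHCG.6.16, show this rate beside the percentages for TEAEs, SAEs, AE discontinuations and each AESI, by treatment group and period.
3. In 6.12.1, extend total patient-years to the LTE and anchor LTE duration on the first LTE injection.
4. In 6.12.7, add the CDI-2 category shift at Weeks 16, 104 and 264 beside the shift to maximum. All three are scheduled CDI-2 visits.
5. Footnote each period's AE collection method and baseline definition.

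No new data are needed; the cost is SAP wording and modest programming. The downside is instability in small cells. Twenty adalimumab patients over the OLT give 20 × 0.307 = about 6.1 patient-years, so a single event is about 16 per 100 patient-years. The interval will show this, and the percentages remain in the table.
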